development of a robust, clinically feasible rsfMRI data analysis pipeline, this study is expected to result in improved understanding of the functional reorganization that takes place during and after intervention.

4. Study Procedures

- Study design, including the sequence and timing of study procedures (distinguish research procedures from those that are part of routine care).

This will be an early phase 1 (phase 0) clinical trial. Specifically, the study will be performed as a randomized, parallel group trial to determine if the amount of changes in brain functional connectivity outcome measures (i.e., between network connectivity) is significantly different between the group of patients that perform FES cycling and another group of patients that perform passive (sham) cycling.

Patients of the International Center for Spinal Cord Injury (ICSCI) at the Kennedy Krieger Institute (KKI) will be identified as meeting the inclusion criteria by reviewing the medical records held by the ICSCI. Once the patient consents by signing the consent form, official screening of subjects will be performed. Subjects will be randomized into 2 groups: FES cycling (Group 1; n=24) and passive cycling (Group 2; n=24). The patients will undergo either an FES cycling or a passive cycling sessions for 4 weeks, 3 times a week. **Acquisition of rsfMRI measures:** MRI will be performed on all participants at the beginning (prior to cycling sessions) and at the end of the 2nd and 4th weeks of the intervention program. **Acquisition of clinical measures:** ISNCSCI and SCIM (Spinal Cord Independence Measure) evaluations will be performed to coincide with the dates of MRI acquisitions, to determine the neurological level and the degree of sensory and motor impairments. Detailed study timeline can be found in Figure 1.

[figure not shown]

Figure 1. Study Timeline.

- SCI patients assigned to FES cycling group will take part in the following evaluations:
 - Medical chart review / MRI screening questionnaire
 - FES cycling trial
 - Neurological evaluation (ISNCSCI – more commonly known as ASIA exam)
 - Functional evaluation (SCIM)
 - MRI

Date: 4.14.2023

Principal Investigator: [name].

Application Number: IRB000182576

E1: FES cycling

- SCI patients assigned to passive cycling group will take part in the following evaluations:
 - A: Medical chart review / MRI screening questionnaire
 - B2: Passive cycling trial

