Patients who are assigned to the passive cycling group will act as a non-treatment group. By comparing the outcome measures of the FES- and Passive-cycling groups, we will be able to determine whether it is the active neuromuscular conduction triggered by FES that leads to alteration in cortical functional connectivity, as opposed to a simple movement of muscles. Physiological effects of FES cycling require treatment for several months. Our proposed study is short (4 weeks). And as such, we expect minimal neurological differences between the FES and passive cycling groups. In contrast, we expect early, observable, and detectable differences in cortical functional connectivity between the FES and passive cycling groups.

- f. Definition of treatment failure or participant removal criteria.

Subjects may withdraw from the study at any time for any reason. Additionally, a subject may be removed from the study for any of the following reasons:

- The subject experiences a medical emergency that necessitates discontinuation of therapy
- The subject experiences a serious adverse event that is judged to be likely related to the assigned treatment group or is of severity that warrants discontinuation of assigned treatment.
- For any medical reason at the discretion of the investigator.
- Subject is not compliant: participants who miss more than 3 sessions of cycling for the duration of the study.
- Subject becomes pregnant.

- g. Description of what happens to participants receiving therapy when study ends or if a participant’s participation in the study ends prematurely.

Upon completion of the study, participants will be referred back to their treating SCI specialist who will be made aware of the treatment and follow-up. The same protocol will be followed for patients who terminate the study early. In the event of discontinuation due to adverse event, participants will be followed by the PI and a medical supervisor of the study ([name]) until resolution or stabilization of their adverse condition and then referred back to their treating SCI specialist.

5. Inclusion/Exclusion Criteria

Only subjects who agree voluntarily to participate in these procedures after they have been fully informed will be included, and who can comprehend the nature of these procedures can participate. Also, their actual involvement will be discussed with them repeatedly to assure adequate knowledge. Subjects will be

Date: 4.14.2023

Principal Investigator: [name].

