Secondary	FES cycling parameters	During intervention	The degree of electrical stimulation is adjusted specifically for each patients, depending on the patients level of sensory and motor impairment, as well as the patient's level of tolerance for sensation and fatigue. Accordingly, the strength and frequency of the electrical stimulation applied during each FES cycling session will be recorded. The duration of the cycling session performed will also be recorded. These parameters may be used as higher-order confounds during statistical data analysis
Secondary	Passive cycling parameters	During intervention	The amount of time and the degree of resistance used by the patients during the passive cycling sessions will be recorded, and may be used as higher-order confounds during statistical data analysis.
Secondary	Personal information	Baseline	Patient's age, sex, handedness, and time since injury will be recorded, and may be used as higher-order confounds during statistical data analysis.
Secondary	SCIM	baseline, mid-intervention, post-intervention	The Spinal Cord Independence Measure Version III (SCIM-III) assesses daily living and mobility activity performances. Specifically, it assesses the degree of self-care (feeding, grooming, bathing, and dressing), respiration and sphincter management, and mobility abilities (bed and transfers and indoors/outdoors) and each category are scored using the SCIM questionnaire. SCIM-III is frequently used in both clinical practice and clinical trial settings and is used to help guide clinicians in determining treatment goals and objectives for patients with an SCI.

c. Statistical plan including sample size justification and interim data analysis.

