Preliminary study: In this preliminary study, we hypothesized that BNC of sensorimotor and visual networks will correlate with the total ISNCSCI score, and performed the study to determine the feasibility of a larger population study. Twelve SCI patients were recruited, and the relationship between the ISNCSCI score and BNC measurements was examined. ISNCSCI sub-scores were first obtained, which were: total upper and lower body motor scores, and total sensory score. The sum of the three scores provided the total ISNCSCI scores. Analysis of the data consisted of preprocessing, PCA, and GICA, and total of 14 intrinsic functional components were identified. BNC between the sensorimotor and visual networks were computed, and plotted against the total ISNCSCI scores. Linear regression analysis was performed to find the best linear fit for the plots. Stronger BNC between the sensorimotor and visual networks was associated with lower total ISNCSCI scores ($R^2=0.35$, $p = 0.04$; [Figure 2](#)[Figure 2](#)). In other words, patients with greater degree of physical impairment tended to have stronger functional connectivity between the sensorimotor and visual networks, suggesting compensatory plastic cortical changes that are related to clinical presentation of the patients. Overall, BNC measures showed good correlations with the total ISNCSCI scores, supporting our hypothesis.

Between network connectivity (BNC) measurements from the above preliminary study provided means, standard deviations, and correlation coefficients for 12 SCI patients. A power analysis¹ revealed that a sample size of 24 subjects will be required to achieve 80% power at an alpha of 0.018; the alpha level was lowered with the correction for multiple comparisons in mind. We will therefore recruit a total of 48 patients. At this point, we do not have enough information about the variability of the BNC in response to the FES to perform a more stringent power analysis. We will use the data in the first 24 SCI subjects recruited to the study to assess the degree of variability in the metric. Based upon these estimates, we will then perform a power analysis to determine how many more subjects will need to be enrolled to assess the significance of our findings.

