The spatial maps of ICA- and SCA-derived brain parcels will be compared across groups. First, the participant-specific sensory and motor brain parcels will be converted to z values, so image intensities reflect the degree to which the parcel is present in each participant's data. The brain parcels will be combined in a second-level random effects analysis using a two sample t-test in SPM8. Voxels that contributed unequally to the parcels across groups will be identified using a liberal voxel-wise p value of 0.01 and a cluster-level p value of 0.05 corrected for multiple comparisons². The between network connectivity (BNC) between sensory and motor parcels will be calculated using Pearson's correlation coefficient between pairs of participant specific motor and sensory brain parcels³. Pairwise-correlations will be converted to Z-scores using Fisher's transformation, and the BNC across groups will be compared using two-sample t tests and adjusted p-values using a false discovery rate correction. Next, we will investigate whether sensory and motor BNC measured at week 2 of cycling program are related to motor and sensory International Standards for Neurological Classification of Spinal Cord Injury (ISNCSCI) scores measured at week 4, using a multivariate linear regression model analysis. Finally, the longitudinal inter- and intra-subject reproducibility of the ICA- and SCA-derived brain parcels will be assessed using intra-class correlation coefficient (ICC).

d. Early stopping rules.

[figure not shown]

Figure 2. Correlations between sensorimotor-visual BNC measurements and total ISNCSCI scores in SCI patients suggest a compensatory plastic cortical changes that are related to clinical presentation of the patients. Patients with lower ISNCSCI score showed larger degree of functional connectivity between the sensorimotor and visual networks.

Date: 4.14.2023

Principal Investigator: [name].

Application Number: IRB000182576

The principal investigator may discontinue the study if the interim statistical analysis as described above indicates that the number of subjects required for this trial exceeds 50.

Patients may withdraw from the study at any time for any reason. Any investigator may discontinue a patient for any of the following reasons:

- The subject experiences a medical emergency that necessitates discontinuation of therapy

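### Section 7.c names no visit for the between-group BNC test, does not say it is on change, and leaves out baseline BNC; a baseline-adjusted regression at one named visit would be more precise at no data cost

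*Combined protocol and SAP*

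**What the plan says.** Section 4.a describes a randomised parallel-group trial, 24 per arm, "to determine if the amount of changes in brain functional connectivity outcome measures" differs between FES and passive cycling. It schedules imaging at three times: "MRI will be performed on all participants at the beginning (prior to cycling sessions) and at the end of the 2nd and 4th weeks". Section 4.e adds that "we expect early, observable, and detectable differences in cortical functional connectivity between the FES and passive cycling groups".

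Section 7.a lists resting-state connectivity as a primary outcome at baseline, mid-intervention and post-intervention, with no primary time point. In 7.c the pairwise correlations are Fisher-transformed, and then "the BNC across groups will be compared using two-sample t tests and adjusted p-values using a false discovery rate correction". That is the whole specification of the between-group BNC test. The next sentence of 7.c does name a visit, "sensory and motor BNC measured at week 2 of cycling program", but for the association with week 4 ISNCSCI scores.

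The personal covariates in 7.b are optional: "age, sex, handedness, and time since injury will be recorded, and may be used as higher-order confounds". Cycling parameters are optional in the same way. Baseline BNC is not listed.

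On sample size, 7.c says that "we do not have enough information about the variability of the BNC in response to the FES" and that it will "use the data in the first 24 SCI subjects recruited to the study to assess the degree of variability in the metric", then recalculate the number needed. Section 7.d lets the principal investigator discontinue if that number exceeds 50.

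**The concern.** This is the randomised comparison that 4.a gives as the reason for the trial, and 7.c leaves two things open.

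- **Which quantity, at which visit.** Change from baseline is the natural reading, given 4.a and the reference in 7.c to variability in response to FES, but 7.c does not say so. The text fits a test of week 2 level, week 4 level, week 2 change or week 4 change. The visit could therefore be picked after the data are seen. A false discovery rate correction controls error only over a family of tests that has been fixed in advance.
- **Baseline BNC.** It is scheduled for every participant but does not enter the model. If baseline and follow-up BNC are correlated, precision from scans already planned is lost.

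The same gap reaches the interim recalculation. The variability to be estimated from the first 24 subjects has no single value until the visit and model are named, and that value feeds the comparison with 50.

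**Working it through.** **Inputs from the documents.** 24 per arm; 80% power; alpha 0.018 (7.c; sidedness not stated, taken as two-sided); scans at weeks 0, 2 and 4.

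**Assumed, because the documents do not give them.** The correlation ρ between baseline and follow-up BNC; the effect size; equal baseline and follow-up SDs.

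**1. The plan's own figure.** The 24 cannot be reproduced for this t test, because no between-group difference or SD is stated. By noncentral t (46 df), 24 per arm at two-sided 0.018 gives 80% power for a difference of 0.955 SD of whatever quantity is tested.

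**2. Relative variance**, with a single-visit t test on level = 1:
- change score: 2(1 − ρ)
- baseline-adjusted regression (ANCOVA): (1 − ρ²) × (1 + 1/44), where 1/44 is the cost of estimating the slope at N = 48
- ratio, ANCOVA to change: (1 + ρ)/2 × 1.023

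| ρ | Change | ANCOVA | Ratio |
|---|---|---|---|
| 0.3 | 1.40 | 0.93 | 0.66 |
| 0.5 | 1.00 | 0.77 | 0.77 |
| 0.7 | 0.60 | 0.52 | 0.87 |

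ANCOVA is more precise than a level test once ρ exceeds √(1 − 1/1.0227) ≈ 0.15. It is more precise than a change test until ρ reaches 2/1.0227 − 1 ≈ 0.96.

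**3. Power at 24 per arm** (46 df for the t test, 45 for ANCOVA). The last two columns set the effect so that the change test has exactly 80% power, that is 0.955 × √(2(1 − ρ)) follow-up SD: 1.13, 0.955 and 0.74.

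| ρ | Change, effect 0.8 follow-up SD | ANCOVA, same effect | ANCOVA where change has 80% | Total N for ANCOVA to reach 80% (change: 48) |
|---|---|---|---|---|
| 0.3 | 46% | 66% | 94% | 34 |
| 0.5 | 63% | 76% | 90% | 38 |
| 0.7 | 86% | 91% | 86% | 44 |

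At ρ = 0.9 the fourth column falls to 81%. Simulation (20,000 trials per cell) agrees with the 0.8 SD powers to within 1 point, and null rejection is 1.8–1.9% for both methods.

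**4. The threshold of 50.** Total N for 80% power, change / ANCOVA:

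| Effect (follow-up SD) | ρ = 0.3 | ρ = 0.5 | ρ = 0.7 |
|---|---|---|---|
| 0.6 | 164 / 108 | 118 / 90 | 72 / 64 |
| 0.7 | 122 / 82 | 88 / 68 | **54 / 48** |
| 0.8 | 94 / 64 | 68 / 54 | 42 / 38 |
| 0.9 | 74 / 52 | **54 / 44** | 34 / 30 |
| 1.0 | **62 / 42** | 46 / 36 | 28 / 26 |

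The answer to whether the number exceeds 50 differs in the 3 bold cells and is the same in the other 12, including all three at 0.8 SD.

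**5. Choice of visit.** Under the null, rejecting if either the week 2 or the week 4 change test has p < 0.018 gives 3.5%, 3.4%, 3.2%, 2.9% and 2.7% when the two change scores correlate 0.3, 0.5, 0.7, 0.8 and 0.9 (200,000 trials). This does not depend on ρ as defined above.

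**The case against.** **Aim 2 in Section 2 already speaks of BNC changes after 2 weeks**, so with 4.a the documents may be said to imply week 2 change, and the gap would be a missing cross-reference. Part of this stands: it supports week 2 as the natural choice. But Aim 2 concerns what happens under FES and its relation to ISNCSCI; it does not fix the visit for the randomised comparison.

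**A t test on change is valid, so ANCOVA is a preference.** It is true that no bias is being corrected. Even so, it is a more precise analysis of data already scheduled, over a wide range of ρ.

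**The gain rests on unstated inputs.** This stands. Aim 1 expects stable BNC under passive cycling, which may point to a high ρ, where the gain is small. Extending the grid to ρ = 0.8 and 0.9 adds no cell in which the threshold answer changes (3 of 25). At ρ = 0.9 and effects of 0.7 to 1.0 SD, ANCOVA needs 2 more participants in total than change (for example 22 against 20), because the lost degree of freedom costs more in small samples. The advantage up to about 0.96 therefore holds at N = 48, not at every N.

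**The error inflation is conditional.** This also stands. If both visits are placed in one Benjamini–Hochberg family at 0.018, simulation gives about 1.5–1.8% under the null. Section 7.c neither includes nor excludes the second visit. Its planned procedure also covers several BNC pairs, so the 1.8% single-test frame is a simplification.

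**One primary visit is not the only remedy.** Testing both visits in a declared family, or a repeated-measures model, would also close the visit gap.

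**Conclusion.** The concern holds. Section 7.c gives no visit, does not carry over the change comparison from 4.a, and omits baseline BNC. The visit and the choice of level or change need stating whatever ρ turns out to be. The covariate is about precision: at 24 per arm, two-sided 0.018 and equal SDs, ANCOVA cuts the variance of a change-score test by 34%, 23% and 13% at assumed ρ of 0.3, 0.5 and 0.7, and gains about 1 point of power at 0.9. The documents supply neither ρ nor an effect size, so the gain cannot be fixed more closely. The effect on the threshold of 50 is limited: most assumed values give the same answer, and 7.d makes stopping discretionary. Nothing here shows that 24 per arm or 48 in total is wrong. The change should be made; confidence in its size is medium.

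**What to change.** In 7.c, replace the BNC t tests with a regression of follow-up Fisher-z BNC on arm and baseline Fisher-z BNC at one named primary visit. Week 2 fits the early-biomarker aim; report week 4 as well. State which BNC pairs and visits form the false discovery rate family, and apply the correction to the p-values for arm from this regression. Use the residual variance of the same model in the interim sample-size calculation from the first 24 subjects; those subjects also give an estimate of ρ.

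The cost is wording and one model term, with no new scans or participants. One degree of freedom is lost, about 2% in variance at N = 48. If ρ is near 0, that is about 1 point of power less than a test of follow-up level (79% against 80% at an effect of 0.955 SD).

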Functional electrical stimulation (FES) cycling is an intervention for SCI patients, in which patterned electrical pulses are delivered to lower extremity muscles to initiate cycling movement. Our group has shown that FES cycling, but not passive cycling (i.e., movement is driven only by the cycle's motor, without electric stimulation), leads to improvements in sensorimotor function, as measured using the International Standard of Neurological Classification for Spinal Cord Injury (ISNCSCI) scoring system. Unfortunately, early detection of response to intervention using ISNCSCI alone is challenging, as observation of clinically significant improvement (increase in ISNCSCI scores) requires at least 4 weeks of intervention. In contrast, previous tfMRI studies have shown that cortical reorganization can be observed after as little as one week of intervention. We hypothesize that reorganization of the sensorimotor cortex underlies neurological and functional recovery during intervention, and that such cortical reorganization will occur prior to observation of clinical improvement. We therefore propose that rsfMRI outcome measures, such as between-network connectivity (BNC; calculated as the degree of temporal dependency between functional networks), can be used to detect early changes in brain functional networks that are predictive of recovery.

Date: 4.14.2023

Principal Investigator: [name].

Application Number: IRB000182576

If successful, these studies will: 1) provide a new and effective clinical tool to study plastic cortical changes that occur after SCI, 2) provide new imaging biomarkers that are predictive of progress towards recovery in response to therapy, and 3) extend our knowledge about the functional reorganization that takes place during and after therapeutic intervention. The developed methods may have broader applications in number of other diseases that affect motor functions, such as stroke and Parkinson's disease.

2. Objectives (include all primary and secondary objectives)

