Aim 1. Characterize the baseline time profile of the rsfMRI outcome measures in chronic SCI patients, acquired over 4 weeks of passive (sham) cycling. In order to quantitatively assess the sensitivity of rsfMRI outcome measures to early functional reorganization that occurs in response to FES cycling, baseline time profile of the outcome measures in the absence of the active stimulation must be established. Accordingly, patients will participate in a 4-week passive cycling program. At weeks 0, 2, and 4, sensory and motor network BNC (calculated using ICA- and SCA-derived brain parcels) and ISNCSCI scores will be measured. *Hypothesis: we will observe stable baseline measures of sensory and motor cortex BNC and ISNCSCI scores of the patients during the 4-week passive cycling program, with minimal to no change in values.*

Aim 2. Characterize the time profile of the cortical reorganization in chronic SCI patients that occurs during a 4-week FES cycling program. *Hypothesis: We will observe early sensorimotor cortex BNC changes after 2 weeks of FES cycling, that are predictive of changes in ISNCSCI scores at week 4.* Specifically, we hypothesize that: a) Changes in sensory network BNC at week 2 will correlate with changes in sensory ISNCSCI scores at week 4; b) Changes in motor network BNC at week 2 will correlate with changes in motor ISNCSCI scores at week 4. To test these hypotheses, we will first measure the sensory and motor network BNC and ISNCSCI scores at weeks 0, 2, and 4, then correlate the changes in sensory and motor network BNC at week 2 with the changes in respective ISNCSCI scores at week 4. Finally, longitudinal (pre- and post- intervention) inter- and intra-subject reproducibility of the ICA- and SCA-derived parcels will be assessed.

3. Background (briefly describe pre-clinical and clinical data, current experience with procedures, drug or device, and any other relevant information to justify the research)

Spinal Cord Injury and Rehabilitation.

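### No planned BNC–ISNCSCI analysis uses the week-2 ISNCSCI taken on the MRI date, so a marker that only mirrors clinical change already present at week 2 could be reported as an early predictor

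*Combined protocol and SAP*

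**What the plan says.** The Abstract (Section 1) hypothesises that "such cortical reorganization will occur prior to observation of clinical improvement". Its supporting premise is that "observation of clinically significant improvement (increase in ISNCSCI scores) requires at least 4 weeks of intervention". Section 3 then justifies a new biomarker by the limited sensitivity of ISNCSCI to early response.

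Aim 2 (Section 2) expects BNC changes after two weeks of FES cycling "that are predictive of changes in ISNCSCI scores at week 4". On data collection it says "we will first measure the sensory and motor network BNC and ISNCSCI scores at weeks 0, 2, and 4", and the study design text in Section 4 says that the clinical "evaluations will be performed to coincide with the dates of MRI acquisitions". Week-2 BNC and week-2 ISNCSCI are therefore concurrent. Section 7a lists ISNCSCI as a primary outcome at mid-intervention too.

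Two analyses link BNC to ISNCSCI:

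- Aim 2 will "correlate the changes in sensory and motor network BNC at week 2 with the changes in respective ISNCSCI scores at week 4".
- Section 7c begins "Next, we will investigate whether sensory and motor BNC measured at week 2 of cycling program are related to motor and sensory International Standards" and ends with "scores measured at week 4, using a multivariate linear regression model analysis".

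Neither names week-2 ISNCSCI as covariate, comparator or outcome. The optional confounders in Section 7b (cycling parameters, age, sex, handedness, time since injury) do not include it. The rest of 7c covers parcel maps, BNC between groups, and reproducibility of parcels.

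**The concern.** The hypothesis has two parts: cortical change comes first, and it predicts the clinical change that follows. The planned analyses address only an association between week-2 imaging and week-4 clinical status.

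Change from week 0 to week 4 is the sum of change from week 0 to week 2 and change from week 2 to week 4. If some patients have already gained ISNCSCI points by week 2, and BNC reflects that gain on the day of the scan, BNC will correlate with week-4 change without leading anything. Adjusting for week-0 values does not help, because the shared component arises after week 0.

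What is at stake is the practical claim. A week-2 MRI is useful for early detection if it tells the clinician something that the week-2 ISNCSCI examination does not. The planned analysis cannot separate a marker that does this from one that does not, and a positive result would be described in the same words either way.

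**Working it through.** **1. The plan's own sample size.** Inputs from 7c: pilot R² = 0.35 in 12 patients, alpha 0.018, power 80%, 24 subjects. The effect size and sidedness behind the 24 are not stated, so I assume the pilot correlation and a two-sided test.

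- |r| = √0.35 = 0.592. With n = 12 this gives p = 0.043, matching the reported 0.04.
- Fisher z: n = ((2.366 + 0.842)/atanh(0.592))² + 3 = (3.207/0.680)² + 3 = 25.2, so 26. A noncentral F calculation gives 23.

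The stated 24 lies between these. It is consistent with a cross-sectional correlation of about 0.59, and I do not dispute it.

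**2. A mirror-only marker.** Let a be the correlation of week-2 BNC change with week-2 ISNCSCI change, and b the correlation of week-2 with week-4 ISNCSCI change. If BNC carries no information beyond week-2 ISNCSCI, its correlation with week-4 ISNCSCI change is r = a × b. Neither a nor b is in the documents; both are assumptions, shown as ranges.

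**3. How often the Aim 2 test declares prediction.** For n = 24 (the FES arm) and two-sided alpha 0.018, the probability is approximately Φ(atanh(r)·√21 − 2.366); the opposite tail adds at most 0.1 percentage point.

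- r = 0.4 × 0.6 = 0.24: 0.245 × 4.583 − 2.366 = −1.244, giving 10.7%.
- r = 0.6 × 0.8 = 0.48: 0.523 × 4.583 − 2.366 = 0.031, giving 51.2%.

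Simulation of the exact t-test (at least 20,000 runs per setting), with and without week-2 ISNCSCI change in the model:

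| a | b | r = ab | Unadjusted | Adjusted |
|---|---|---|---|---|
| 0.3 | 0.5 | 0.15 | 5% | 1.9% |
| 0.3 | 0.9 | 0.27 | 14% | 2.0% |
| 0.4 | 0.6 | 0.24 | 11% | 1.8% |
| 0.59 | 0.7 | 0.41 | 37% | 1.8% |
| 0.6 | 0.8 | 0.48 | 52% | 1.9% |

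7c does not say which arms enter the regression. If both were pooled (n = 48), the unadjusted range would be about 23–88% for a = 0.4–0.6 with b = 0.6–0.8, and 9–31% for a = 0.3 with b = 0.5–0.9.

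**4. What this does not cover.** The figures apply to the change-on-change correlation in Aim 2. Section 7c reads as week-2 levels against week-4 levels, and I have not quantified that test. The simulation also treats week-2 ISNCSCI as measured without error.

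**The case against.** The strongest reply is that week-2 ISNCSCI may hardly move. The Abstract says clinically significant gains take at least four weeks, and Section 4e expects minimal neurological differences between the arms over the whole study. If so, week-2 change is small and mostly measurement noise, which BNC has little to mirror. In addition, week-2 and week-4 change scores share the week-0 measurement, so part of b may be baseline error that BNC cannot track. This stands as a reason to take the weak-link figures seriously. It does not remove the point: the premise concerns clinically significant gains, smaller score changes at week 2 are not excluded, and the plan has the data to check but no analysis that does.

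A second reply is that adjustment is not a clean test of precedence. If BNC shifts early and ISNCSCI follows before week 2, the covariate lies on the pathway and removes genuine early signal. That is right. The adjusted coefficient measures value beyond same-day ISNCSCI, not order in time, so both models should be reported.

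A reader might infer that week-2 ISNCSCI is not used anywhere. The documents do not support that: Aim 1 expects stable scores at weeks 0, 2 and 4 under passive cycling, and 7a lists the mid-intervention score as primary. But Aim 1 concerns the passive arm, 7c gives no method for it, and it does not test precedence under FES.

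A reader might also work at alpha 0.05, where the same inputs give about 20–69%. The plan sizes the study at 0.018, so the lower figures are the relevant ones.

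**Conclusion.** The point holds in this form: neither BNC–ISNCSCI analysis uses the concurrent week-2 ISNCSCI, so the plan, followed exactly, could present a mirror of same-day clinical change as early prediction. For the Aim 2 test with 24 patients at alpha 0.018, the chance of this for a mirror-only marker is about 11–52% under moderate links and about 5–14% under a weak first link, against about 1.8% with adjustment. These rates rest on assumed correlations and on the marker having no added information. They do not say that BNC is such a marker. The pilot association in 7c makes a same-day link plausible but no more, since it compares levels rather than changes and uses sensorimotor–visual connectivity. I class this as a cheap improvement.

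**What to change.** In 7c, add to the Aim 2 analysis a model of week-4 ISNCSCI change on week-2 BNC change, sensory with sensory and motor with motor, with the matching week-0-to-week-2 ISNCSCI change as a covariate. Report it beside the unadjusted correlation, and claim value beyond week-2 ISNCSCI only if the adjusted BNC coefficient supports it. Also report week-0-to-week-2 ISNCSCI change in the FES arm next to week-2 BNC change, so that the claim of precedence is checked against data.

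Replacing the covariate by an outcome of week-2-to-week-4 change is not an equivalent shortcut. With week-2 change left out of the model and equal standard deviations, a mirror-only marker (a = 0.6, b = 0.6, n = 24, alpha 0.05) is still declared significant in about 25% of trials, against 5% with the covariate.

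The cost is wording only, because the data are already scheduled. The downsides are one more model term, some loss of power, possible removal of real early signal if BNC change drove ISNCSCI change before week 2, and some residual confounding where week-2 ISNCSCI is measured with error.
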